Outcome assessment will occur at 3 weeks (treatment midpoint), 12 weeks (post-treatment), and 15 weeks (follow-up). Housing status and participation in work/school will be assessed by telephone monthly for 12 months following program discharge. Healthcare appointment attendance rates during the 12-month follow up period will be ascertained from CPRS records. We will maximize our data collection efforts by gathering participant cell phone numbers (most O/O/O Veterans, even those who are homeless, have cell phones). Furthermore, at baseline and discharge, we will obtain contact information for the Veteran and for at least two family members and close associates who can be contacted in case the Veteran cannot be contacted for monthly follow-up assessments of housing status. In the event that the Veteran still cannot be reached by telephone, we will use CPRS to track housing status (e.g., via V codes and progress notes), with appropriate HIPAA consent.

Table 1. Experimental and Control Conditions

Compensatory Cognitive Training (Appendix 1)	Education Control (Appendix 2)

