as Random Regression Modeling and Hierarchical Linear Modeling) which takes advantage of all existing data points for minimal loss of data, will be used to analyze the data related to our main hypothesis (H1a). Therefore, we will not impute missing data because our analytic method uses all existing data points, including all subjects with missing data or those who were terminated early in the study, without relying on data imputation procedures (Diggle et al., 1994; Laird & Ware, 1982; Hedeker et al., 1991). The mixed effects approach provides more information and, therefore, more power compared to cross-sectional analyses that focus on the analysis of one summary index or more traditional analytic approaches such as a change score, end-point, or repeated measures analysis of variance (ANOVA). We will also use pattern-mixture models to assess if there is bias due to drop out or missing data. As described by Hedeker and Gibbons (1997), these mixed models allow us to assess whether important estimates are dependent on missing data patterns, and provide overall estimates of effects by averaging over the various missing-data patterns. In addition, we will consider the extension of the Pattern-Mixture models as described by Guo et al. (2004), which includes the incorporation of random effects in the pattern mixture model, allowing subject-to-subject heterogeneity. Missing data will be examined to assess randomness. The pattern of missing data will be examined according to the procedure recommended by Little and Rubin (1987), which includes comparing group differences in the primary outcomes of subjects with versus without missing data. SPSS and SAS statistical software will be used to analyze the data. Type I error will be controlled by a Bonferroni adjustment to the alpha per outcome domain for Hypotheses 1a and 1b. Specific plans for testing each hypothesis are below.

H1a: Positive CCT-associated effects on cognition, functional capacity (co-primary outcomes), and disability will emerge over the 15-week study.

Dependent variables: Cognition (global deficit score [GDS] composite; Heaton, et al., 1995), UPSA-B (co-primary outcomes), WHODAS 2.0.

Independent variables: Treatment group (CCT vs education control) and Time (0, 5, 10, 15 weeks).

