Dependent variables: Proportion of months housed, proportion of months engaged in productive activity (work or school), and proportion of VA healthcare appointments attended during the 1-year follow up period (all three outcomes based on monthly data collected during the 1-year follow-up period). Any missing data on housing and work/school status will be accounted for by using a proportion based on the available data points. Healthcare appointment attendance will be gathered from CPRS data and will not be subject to missing data.

Independent variable: Treatment group (CCT vs education control).

Statistical analyses: ANOVA models comparing the treatment and control group on the three dependent variables above. We have selected ANOVA over alternative models (t-test; Wilcoxon Rank Sum; Poisson regression) due to the type of dependent variables (continuous) and the option to include any covariates that might be imbalanced between the treatment groups.

Power analysis: With 78 subjects (39 subjects per group), we will have .80 power to detect an effect size of .64, a medium-to-large effect size.

capacity, disability, and community reintegration.

Dependent variables: UPSA-B at 15 weeks, WHODAS 2.0 at 15 weeks, proportion of months housed, proportion of months engaged in productive activity (work or school), and proportion of VA healthcare appointments attended during the 1-year follow up period.

Independent variables: Treatment group (CCT vs education control).

Mediators: Cognitive improvement in GDS composite from 0-10 weeks (slope of change across weeks), improvement in CPSA cognitive strategy use from 0-10 weeks (slope of change across weeks).

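### The H1b housing and work/school proportions drop unobserved months with no H1b sensitivity analysis, which can bias the arm comparison, most clearly for work/school.

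*Combined protocol and SAP*

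**What the plan says.** All references are to Section 9 (Design and Methods) of the combined protocol and SAP.

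- **Collection (Procedure).** "Housing status and participation in work/school will be assessed by telephone monthly for 12 months following program discharge".
- **Back-up sources (Procedure).** At least two relatives or associates are recorded "who can be contacted in case the Veteran cannot be contacted for monthly follow-up assessments of housing status". After that: "In the event that the Veteran still cannot be reached by telephone, we will use CPRS to track housing status". Both name housing status. Neither names work or school.
- **Missing-data rule (H1b, dependent variables).** "Any missing data on housing and work/school status will be accounted for by using a proportion based on the available data points". No minimum number of months is set, and nothing is said about a participant with no observed month.
- **Analysis (H1b).** "ANOVA models comparing the treatment and control group on the three dependent variables above", that is, one proportion per person.
- **Third H1b outcome.** "Healthcare appointment attendance will be gathered from CPRS data and will not be subject to missing data". It is outside this point.
- **Missing-data methods (Analytic Plan and Power Analyses).** "We will also use pattern-mixture models to assess if there is bias due to drop out or missing data". This stands in the description of the mixed models for H1a. The missing-pattern check that follows, "which includes comparing group differences in the primary outcomes of subjects with versus without missing data", concerns the primary outcomes, and H1a names those as the GDS composite and the UPSA-B.

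**The concern.** Dividing by observed months gives the right answer only if a month's chance of being observed is unrelated to housing or work in that month. The main source is a telephone call to people who were homeless or unstably housed at entry. It is an inference, but a plausible one, that a Veteran who loses housing or a job is harder to reach. CCT teaches prospective memory and organisation, so reachability could also differ by arm.

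If so, the arms are compared on differently selected months. The same proportions are dependent variables in the H2 mediation and Aim 3 moderation analyses, so a distortion would carry through. Nothing pre-specified for H1b would show it.

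**Working it through.** **The plan's own figure.** H1b claims .80 power for an effect size of .64 with 39 per group. At an unadjusted two-sided .05: 0.64 × √(39/2) − 1.96 = 2.826 − 1.960 = 0.866, and Φ(0.866) = .807 (noncentral t: .797). The figure reproduces and assumes complete outcome data. The plan also applies a Bonferroni adjustment to H1b without stating the divisor, so I show .05 and an assumed .05/3.

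**Inputs.** From the plan: 39 per arm, 12 monthly observations, one proportion per person, two-group comparison. Assumed, because the documents give no values: the true share of months housed (p), the chance that a month is observed when housed (rH = .9), and the chance when unhoused (rU, varied). For work/school, read *in work or school* for *housed*.

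**Month-level formula.** Expected observed share = p·rH / [p·rH + (1 − p)·rU].

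No true effect, p = .70 in both arms:
- rU .8 in CCT: .63/(.63 + .24) = .724. rU .5 in control: .63/(.63 + .15) = .808. Difference −8.4 points.
- rU .7 in CCT: .63/(.63 + .21) = .750. rU .3 in control: .63/(.63 + .09) = .875. Difference −12.5 points.
- Equal rU in both arms: difference 0.

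This formula pools months, so people with more known months count more. The plan averages one proportion per person. To follow the plan I simulated individuals: housing propensity Beta-distributed with mean p and concentration 1.5, months independent given the person, t-test between arms, at least 4,000 runs per scenario.

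| True share, CCT vs control | rU, CCT vs control | Recovery of missed months | Observed difference (points) | Rejection at .05 |
|---|---|---|---|---|
| 70% vs 70% | .8 vs .5 | none | −5.4 to −5.7 | 13–14% |
| 70% vs 70% | .8 vs .5 | half | about −2 | 6% |
| 70% vs 70% | .7 vs .3 | none | about −9 | 30–32% |
| 70% vs 70% | .7 vs .3 | half | about −3 | 8% |
| 80% vs 60% | .3 vs .3 | none | 14 (true 20) | .67–.68 (complete data .82–.83) |
| 80% vs 60% | .8 vs .4 | none | 10 (true 20) | .31–.33 |
| 40% vs 20% | .3 vs .3 | none | 24 (true 20) | not the point here |

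At .05/3 the first row rejects about 6%. That is still about 3.5 times its nominal rate (5.9/1.67).

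**Direction under equal loss.** By the formula with rU = .3, 80% vs 60% becomes .72/.78 − .54/.66 = .923 − .818 = 10.5 points (14 per person). By the same formula 40% vs 20% becomes .36/.54 − .18/.42 = .667 − .429 = 23.8 points (24 per person). The effect shrinks at high base rates and grows at low ones.

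**Weighting by months known.** This moves the estimate toward the pooled formula: from about −5.6 to about −8.4 points in the first null scenario, and from about −9 to about −12.5 in the second. False positives rise from 13% to 26% and from 32% to 63%.

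**Back-fill at the next successful contact.** In the −9 point scenario the false difference falls to −0.8 or −0.9 points and rejection returns to 5%. This assumes accurate recall and a later contact.

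**The case against.** The strongest reply is that the plan already provides for unreached Veterans. A reader might infer from the H1b rule that housing is counted only in months when the Veteran answered the telephone. The Procedure text does not support that: relatives, associates and CPRS supply housing data when the Veteran is not reached. If they recover 80% of missed months, the first scenario falls to about 1 point with rejection near 5%. This stands for housing, though recovery may be incomplete and CPRS entries may depend on engagement with VA care. It does not help work/school, which has no stated back-up.

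Second, the plan does promise pattern-mixture models and an examination of whether missing data are random. Those models belong to the H1a mixed-model analysis, and the pattern check concerns the primary outcomes. Neither changes nor bounds an H1b estimate from ANOVA on per-person proportions.

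Third, every contact rate here is assumed, and the larger rejection rates combine no recovery with an unadjusted alpha. That is correct; they illustrate the mechanism and do not predict the trial's error rate.

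Fourth, it is tempting to call it a defect that a Veteran known for one month counts as much as one known for twelve. Under this mechanism equal weighting limits the bias, so the complaint should not be made.

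**Conclusion.** The point holds as a conditional one. As written, the rule can give a wrong H1b result if observation depends on status, and no H1b analysis is planned that would reveal it. The exposure is clearest for work/school and smaller for housing. Under the assumptions above, loss that differs by arm produces a false difference of about 6 to 9 points without recovery and about 2 to 3 points if half of the missed months are recovered.

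Two stronger readings go too far. A reader might infer that the rule will bias the comparison, or will manufacture a benefit for CCT. The documents give no contact rates by arm or status, and equal loss leaves a true null at zero. If CCT improves reachability, the null scenarios here bias against CCT; the reverse pattern would favour it. A reader might also infer that equal loss always dilutes a true effect, but the direction depends on base rates that the documents do not give.

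H1b is a named hypothesis but not co-primary, so this is a change that should be made rather than a flaw in the primary analysis.

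**What to change.** 1. **Collect the missed months.** At each successful call, or contact with a named relative or associate, ask housing and work/school status for every month since the last contact. Use the associates and CPRS for work/school as well as housing. The residential timeline follow-back already used at intake (Table 2) offers a format for housing; work/school needs a parallel question.
2. **Pre-specify for H1b**, before unblinding, a sensitivity analysis that counts unresolved months as not housed or not working, and a tipping-point analysis that varies the assumed status of unresolved months separately by arm. The first also settles how a participant with no observed month is handled. Treat it as a bound, not as the best estimate.
3. **Report** months observed and data source (Veteran, associate, CPRS) by arm for each outcome.

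Do not weight by months known, and do not offer a month-level GEE as the remedy. Neither addresses status-dependent observation, and weighting by months known enlarges the false difference in the null scenarios.

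The cost is one or two questions on an existing call, plus analysis wording. Recalled months are less accurate than current-month reports, especially in a sample selected for cognitive impairment. Back-fill does not recover Veterans permanently lost to contact, so item 2 is needed even if item 1 is adopted.

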The sole recruitment source for this study will be the VA Aspire Center, a 40-bed Residential Rehabilitation Treatment Program serving homeless O/O/O Veterans with mental health conditions such as PTSD, depression, and TBI. A rate of accrual of 10 participants enrolled per quarter during the recruitment period (last three quarters of Year 1; Year 2; first quarter of Year 3) would be required to support our targeted accrual. The average length of stay is 3-6 months, meaning that between 80 and 160 participants per year would be eligible for the study. We aim to enroll 30 participants in the last three quarters of Year 1, 40 in Year 2, and 10 in the first quarter of Year 3, making our enrollment goals feasible. Our research team has held several planning meetings with the Aspire Center team and has identified a plan for successful recruitment that maximizes the possibility that participants will be enrolled while being minimally disruptive to Aspire Center operations. To facilitate recruitment, our PI and study staff will be highly visible at the Aspire Center and will coordinate with program intake staff (please see Letter of Support from [name], LCSW, Chief of the Aspire Center). Individuals who meet the inclusion criteria outlined above will then be approached for potential participation in the study and, if interested, will complete the consenting process and the baseline assessment.

Retention

During the trial, assessments will be administered at baseline, 5 weeks, 10 weeks, and 15 weeks, and brief monthly follow-up phone calls will assess housing and employment/education status for one year following program discharge. Participants will be compensated for their time spent in assessments (\$25 per assessment X 4 assessments = \$100 maximum total compensation) as a way to enhance retention. Based on prior studies of Veterans with PTSD and/or TBI, we expect about 20% attrition, for a final sample size of 78 (39 per group). Attrition may be even lower, given that all participants will be residing on-site. Monthly follow-up assessment of housing/employment status will be brief and not burdensome to participants.

Procedure

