Statistical analyses: We will analyze data on all randomized subjects with a baseline assessment and at least one post-baseline evaluation, using mixed effects models, described above. The mixed effects model method provides an estimate of the individual variability around the population trend, the variability of the individual intercepts (baseline values) and slopes (changes across time), and the correlation between them. A fully saturated treatment by time model will be utilized for inference. Covariance structure will be chosen based on Akaike's Information Criterion (AIC). Random group level treatment effects will also be evaluated for importance based on the model AIC. This method allows for any group level effects to be incorporated into the model. Denominator degrees of freedom will be calculated using the Kenward-Roger small sample correction.

Power Analysis: We used procedures described by Hedeker et al. (1999) for Random Regression Models for the proposed study to estimate needed sample size (the RMASS program provided by Hedeker). We estimated that with a final sample size of 78 (target n=98, with a drop-out rate of 20%), the study will have .80 power to yield a statistically significant result for a .72 effect size, accounting for Type I error correction, .5 correlation between time points, and one random effect in the model. We have previously found CCT-associated effect sizes of .72 for prospective memory functioning in Veterans with mild to moderate TBI (74% of whom had PTSD), as well as for the UPSA-B in individuals with severe mental illness. Although we have not previously used the WHODAS 2.0 to assess disability, we have also found CCT-associated effect sizes of .81-1.0 for quality of life in these populations. The trial was therefore powered to detect effect sizes in the .72 range.

H1b: Positive CCT-associated effects on community reintegration outcomes (housing stability, participation in employment/education, healthcare appointment attendance) will be detected at the end of the 1-year follow-up.

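### The H1b power figure (.80 at an effect of .64) matches an uncorrected two-sided alpha of .05, although the plan Bonferroni-adjusts H1b

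*Combined protocol and SAP*

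**What the plan says.** All the relevant text is in Section 9, under Analytic Plan and Power Analyses.

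- **Multiplicity rule**, in the general analysis text before the individual hypotheses: "Type I error will be controlled by a Bonferroni adjustment to the alpha per outcome domain for Hypotheses 1a and 1b". The rule gives no overall alpha, sidedness or divisor, and does not define an outcome domain.
- **H1b analysis**: "ANOVA models comparing the treatment and control group on the three dependent variables above". The three variables are the proportion of months housed, the proportion of months in work or school, and the proportion of VA appointments attended.
- **H1b power**: "With 78 subjects (39 subjects per group), we will have .80 power to detect an effect size of .64, a medium-to-large effect size". No alpha and no correction are mentioned.
- **H1a power**, for contrast: "the study will have .80 power to yield a statistically significant result for a .72 effect size, accounting for Type I error correction".
- **Source of the 78** (Retention): "we expect about 20% attrition, for a final sample size of 78 (39 per group").
- **Missing data for one H1b outcome**: "Healthcare appointment attendance will be gathered from CPRS data and will not be subject to missing data".

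**The concern.** The plan commits to a stricter significance threshold for H1b, but the H1b power line seems to have been computed without it. The H1a line says that the correction is included. The H1b line is silent, and its numbers are those of an ordinary test at .05.

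Two things are at stake. First, if H1b is tested at the adjusted alpha, the chance of missing an effect of .64 is larger than the 20% that the plan implies, and a null result on housing or employment would be read against a power claim that the planned test does not support. Second, because the alpha, sidedness and divisor are nowhere printed, the threshold for declaring an H1b result significant is not fixed in advance.

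**Working it through.** **Inputs from the plan.** 39 analysed per group (98 × 0.8 = 78.4, taken as 78); standardized effect .64; stated power .80; three H1b outcomes; a Bonferroni adjustment that names H1b.

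**Inputs assumed.** Overall alpha .05, two-sided. The hypothesis is worded directionally, but no one-sided test is specified and the ANOVA F test is non-directional.

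**Formula.** A two-group ANOVA without covariates is equivalent to a two-sample t test. With n per group, df = 2n − 2 and noncentrality δ = d·√(n/2). Power is P(T > t_crit), where T is noncentral t with df and δ, and t_crit is the 1 − α/2 quantile of central t. The opposite tail is negligible.

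**Step 1: reproduce the printed figure.** n = 39, df = 76, δ = .64 × √19.5 = 2.826. At two-sided .05, t_crit = 1.992 and power = .797. The effect detectable with .80 power is .643. Solving instead for the two-sided alpha that gives exactly .80 at .64 returns .0513. The printed line is therefore a calculation at .05 with no correction.

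**Step 2: apply the adjustment at 39 per group, two-sided.**

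| Divisor | Alpha | t_crit | Power at .64 | Effect detectable at .80 power |
|---|---|---|---|---|
| 1 | .05 | 1.992 | .797 | .643 |
| 2 | .025 | 2.287 | .705 | .710 |
| 3 | .0167 | 2.448 | .648 | .747 |
| 4 | .0125 | 2.559 | .607 | .772 |

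With divisor 3 the shortfall against the printed figure is .80 − .648 ≈ .15.

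**Step 3: one-sided variants at 39 per group.** One-sided .05/2 has the same critical value as two-sided .05, so it also gives .797 and .643. One-sided .05/3 gives .744 and .683.

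**Step 4: appointment attendance on all 98.** With n = 49 per group, δ = .64 × √24.5 = 3.168. Two-sided .05/3 gives power .766 at .64 and a detectable effect of .664; two-sided .05/2 gives .812 and .631.

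**Step 5: scale.** Keeping .80 power at .64 with two-sided alpha .0167 would need 53 analysed per group (52 gives just under .80, at .795).

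**The case against.** The strongest reply is that the divisor of 3 is inferred. If housing, work or school, and appointment attendance each form their own domain with one measure, an adjustment within domains has divisor 1 and .64 stands. The text does not strictly exclude this. But it would mean that H1b receives no adjustment at all, although the rule names H1b. If that is what the sponsor intends, the plan needs to say so. The point also does not depend on choosing 3, because every two-sided divisor above 1 lowers power at 39 per group to about .70 or less. One-sided .05 over two tests would rescue the figure too, but the plan states no one-sided test and H1b has three outcomes.

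A second reply is that 39 per group may be too few. Attendance comes from records. Missing housing and work or school months are handled by using whatever months are available, and the Procedure text allows contacts and records to be used to establish housing status. Housing could therefore also exceed 39 per group, and at 49 per group with divisor 3 the shortfall would be about 3 points (.766 against .80). This stands as a limit on the size of the problem. It does not rescue the printed line, which is explicitly for 78 subjects. Nor is 98 assured for any outcome, since participants who fail the effort test leave the remainder of the study.

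Third, the H1a effect of .72 comes from a four-time-point mixed model and from cognitive and functional measures. Comparing it with an H1b effect carries little weight, and nothing here relies on it beyond the observation that one power line mentions the correction and the other does not.

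Finally, the plan's arithmetic is sound at alpha .05. The fault is that this is not the alpha to which the plan commits.

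**Conclusion.** The concern holds. The H1b power figure reproduces at an uncorrected two-sided .05 and is inconsistent with the plan's own Bonferroni rule for H1b. Assuming overall two-sided .05, three tests and 39 analysed per group, power at .64 is about .65 rather than .80, and the effect detectable with .80 power is about .75 rather than .64. Across divisors 2 to 4, power ranges from .70 to .61 and the detectable effect from .71 to .77. That the printed number reflects no two-sided correction is certain; the exact corrected value is not, because the plan leaves the divisor and sidedness open.

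The consequence is limited. H1b is not co-primary, the sample size is justified through H1a, and no test changes. The figure should still be corrected, because it tells readers how to interpret a null H1b result.

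**What to change.** State the overall alpha, the sidedness and the Bonferroni divisor for H1b, define what counts as an outcome domain, and restate the power at the resulting alpha. Under two-sided .05/3 the line could read: *with 39 per group and two-sided alpha .0167, power is .80 for an effect of about .75 and about .65 for an effect of .64*. If the sponsor intends no correction across the three H1b outcomes, say so and label the existing figure as unadjusted.

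If appointment attendance will be analysed on all 98 randomized, give its figure separately: under the same alpha, .80 power for about .66, or about .77 at .64. The same should be done for housing if its analysed number is expected to exceed 39 per group.

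The cost is wording and a less favourable stated power for H1b. No change to sample size, data collection or tests is needed; the 53 per group in the working is given for scale only and is not proposed.
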